13.5 Direct Access to Source Documents and Monitoring

13.5.1 Direct Access to Source Documents

The head of the trial site and the investigator must accept monitoring and audits to be performed by the sponsor and inspection by the IRB and Japanese and foreign regulatory authorities, and must make source documents and all other trial-related records available to these agencies for direct access (including copying). Subjects authorize such direct access by signing the written ICF.

13.5.2 Monitoring

The sponsor bears responsibility for ethical, legal, and scientific conduct of the trial. The sponsor will perform monitoring according to the “Procedures for monitoring” specified for this trial. Monitoring includes periodic visits, phone calls, or other contact with the trial site for the provision, obtaining, and recording of updated trial-related information by monitors designated by the sponsor.

The sponsor may entrust a portion of monitoring activity to a contract research organization.

13.5.3 Documents to Be Retained by the Investigator

The trial-related documents to be retained by the investigator will be kept in the investigator’s file, which will be managed by the investigator.

13.6 Deviations From and Changes or Amendments to the Trial Protocol

13.6.1 Deviations From the Trial Protocol

- 1) The investigator or subinvestigator should not deviate from the protocol or change it without prior written agreement between the investigator and the sponsor and the written approval of the IRB of the trial site based on prior review.
- 2) In unavoidable medical circumstances such as the need to avoid emergent risk to a subject, the investigator or subinvestigator may deviate from the protocol or change the protocol without prior written agreement from the sponsor and prior approval of the IRB. In such an event, the investigator will promptly submit a document providing the details of and reason for the deviation or change to the sponsor and the head of the trial site and obtain approval from the IRB. In addition, the investigator will obtain written approval from the head of the trial site and the written agreement of the sponsor by way of the head of the trial site.
- 3) The investigator or subinvestigator will record all deviations from the protocol.

13.6.2 Amendments to the Trial Protocol

- 1) The investigator will promptly submit to the sponsor, the head of the trial site, and the IRB by way of the head of the trial site, a written report on any changes in the trial that may significantly affect conduct of the trial or increase risks to the trial subjects.
- 2) The sponsor, after conferring with the investigator, will agree with the investigator on the contents of the revised protocol and compliance with the revised protocol.
- 3) The sponsor will promptly submit the revised protocol to the head of the trial site.

13.7 Archiving of Records

- 1) The investigator and the trial site will retain all the trial-related documents and records for the period of time indicated in a) or b) below, whichever is longer. However, if the sponsor requires a longer period of archiving, the head of the trial site will consult with the sponsor on the period and procedures of record retention.
 - a) A period of at least 3 years following the manufacturing and marketing approval of OCV-501; or, if the head of the trial site receives notification from the sponsor that development has been terminated or that results of the trial will not be submitted with the approval application, the date 3 years after receipt of such notification.
 - b) The date 3 years after termination or completion of the trial.
- 2) The investigator will retain the trial-related documents and records as directed by the head of the trial site.
- 3) If it becomes no longer necessary to retain the trial-related documents and records at the trial site, the sponsor will notify the head of the trial site.

13.8 Termination or Interruption of Part or All of the Trial

13.8.1 Termination or Interruption of the Trial at Individual Trial Sites

- 1) In the event of termination or interruption of the trial, the investigator will promptly provide the head of the trial site with written notification and a written explanation of the details of the termination or interruption of the trial.
- 2) When the sponsor has been informed by the head of a trial site that the investigator has terminated or interrupted the trial, the sponsor will obtain a detailed written explanation of the termination or interruption of the trial from the head of the trial site.

13.8.2 Termination or Interruption of the Entire Trial

- 1) When the entire trial is to be terminated or interrupted by the sponsor, the sponsor will promptly provide the heads of all trial sites involved in the trial and the

regulatory authority with written notification and a detailed written explanation of the reason for the termination or interruption of the trial.

- 2) When the investigator has received notification of termination or interruption of the entire trial by the sponsor from the head of the trial site, the investigator will obtain a detailed written explanation of the termination or interruption of the trial from the head of the trial site, promptly notify the trial subjects currently receiving IMP administration, and take necessary measures such as switching to appropriate alternative treatment(s).
- 3) When development of the IMP is terminated by the sponsor, the sponsor will promptly provide the heads and the investigators of all trial sites involved in the trial and the regulatory authority with written notification and a detailed written explanation of the reason for the termination of development.

13.9 Protection of Subjects' Personal Information

In completion and handling of CRFs, the investigator and subinvestigator will take adequate care to ensure protection of the personal information of subjects. Individual subjects will be identified by subject numbers. The sponsor will not provide the information obtained to any third party.

As this trial will involve HLA genotyping, genetic information will be handled carefully and appropriately in consideration of the particularity of the information, even if it is not categorized as personal information due to being coded.

13.10 Compensation for Injury to Health

Trial subjects will be compensated for health damages according to the criteria established by the trial sponsor with reference to applicable regional regulatory requirement(s) for this trial will comprise medical costs and medical benefits.

CS	Compound symmetry
CSH	Heterogeneous CS
CTCAE	Common Terminology Criteria for Adverse Events
DFS	Disease-free survival
ECG	Electrocardiogram
ECOG	Eastern Cooperative Oncology Group
eCRF	Electronic case report form
EORTC QLQ-C30	The European Organization for Research and Treatment of Cancer QLQ-C30
FAS	Full analysis set
HF	Harrington-Fleming
IFN- γ	Interferon gamma
HR	Hazard ratio
IRS	Immune response set
IMP	Investigational medicinal product
IVRS	Interactive Voice Response Services
IWRS	Interactive Web Response Services
LS	Least squares
MedDRA	Medical Dictionary for Regulatory Activities (The ICH international medical dictionary)
MMRM	Mixed-effect model repeated measures
OS	Overall survival
PPS	Per protocol set
PS	Performance status
PT	Preferred term
QTc	Corrected QT interval
QTcF	QT interval as corrected by Fridericia's formula
QOL	Quality of life
REML	Restricted maximum likelihood
RS	Raw score
SAE	Serious adverse event
SD	Standard deviation
SOC	System organ class
SS	Safety analysis set
TOEP	Toeplitz

Abbreviation	Expansion
UN	Unstructured
VC	Variance Components
WHO-DD	World Health Organization Drug Dictionary
WT1	Wilm's tumor gene 1

1 INTRODUCTION

OCV-501 is a drug product containing an HLA class II restricted Wilm's tumor gene 1 (WT1) derived peptide.

In the phase 1 trial (Trial 311-10-001), OCV-501 was subcutaneously administered once a week for 4 times at doses of 0.3 mg, 1 mg, and 3 mg in elderly acute myeloid leukemia (AML) patients and safety and tolerability of OCV-501 were assessed. In this phase 1 trial, no dose-limiting toxicities were reported and the tolerability of OCV-501 treatment up to a dose of 3 mg was confirmed. In addition, OCV-501 specific delayed-type hypersensitivity was observed at each dose. This finding suggests that OCV-501 induces the T cell mediated immune response.

This trial is planned as a randomized placebo-controlled comparative trial, to assess the efficacy and safety of OCV-501 treatment as a maintenance therapy in elderly patients with AML who have completed consolidation therapy after being judged to have achieved complete remission following an induction regimen.

This statistical analysis plan is based upon the following study documents:

- Study protocol,
- Electronic case report form (eCRF)

2 TRIAL OBJECTIVES

The primary objective is to compare the disease-free survival (DFS) in AML patients 60 years or older, who are randomly assigned to receive either OCV-501 monotherapy or placebo.

The secondary objectives are:

- To compare overall survival (OS) between both treatment arms
- To compare patient quality of life (QOL) (European Organization for Research and Treatment of Cancer [EORTC] QLQ-C30) and performance status (PS; Eastern Cooperative Oncology Group performance status [ECOG PS]) between both treatment arms
- To characterize and compare safety in both treatment arms
- To assess immunological responses (OCV-501 specific interferon gamma [IFN- γ] production, WT1-killer peptide specific IFN- γ production, anti-OCV-501 antibody level, anti-WT1 antibody level, immunoglobulin)
- To assess WT1 mRNA level

3 INVESTIGATIONAL PLAN

3.1 Overall Study Design and Plan

This trial is a multinational, multicenter, randomized, double-blind, placebo-controlled trial in elderly patients with AML, to compare DFS in patients 60 years or older with AML who are randomly assigned to receive either OCV-501 monotherapy or placebo.

This trial consists of the following three periods.

3.1.1 Screening Period

The eligible patients will be randomly assigned to one of the following treatment arms at a ratio of 1:1

- OCV-501 arm: 3 mg of OCV-501 (0.4 mL)
- Placebo arm: Placebo (0.4 mL)

The patients will be assigned to either treatment arm via the interactive voice response services (IVRS) or the interactive web response services (IWRS).

3.1.2 Treatment Period

From Week 1 to Week 104, the investigational medicinal product (IMP) will be subcutaneously administered: once-weekly up to the 8th administration, and every two weeks from the 9th administration onward.

Blood sampling for expressed level of WT1mRNA, anti-OCV-501 antibody, anti-WT1 antibody, and immunoglobulin will be performed at least once every four weeks.

OCV-501 specific IFN- γ production, WT1-killer peptide specific IFN- γ production will be assessed at Week 5, Week 9, Week 13, and every 12 weeks.

QOL and PS will be measured at least once every 4 weeks. A concomitant drug survey will be performed at every scheduled visit. For the safety of the subjects, a medical interview, blood biochemical tests, urinalysis, and adverse event (AE) observation will be performed. Vital signs, body weight, and 12-lead electrocardiogram (ECG) will be measured.

Retrospective evaluation of samples will be conducted by the central pathological review committee. The central pathological review committee will evaluate the sample used at the judgment of relapse by the trial site and the previous sample from before relapse, and verify the judgment of relapse of the trial site.

3.1.3 Post-treatment Observation Period

Subjects will return to the trial site 11 to 17 days after the last dose of the 2-year IMP administration period to undergo a completion examination during the post-treatment observation period. If a patient discontinues IMP administration before completion of the 2-year treatment period, the patient will undergo a withdrawal examination within 7 days after the investigator or sub-investigator judged withdrawal to be necessary.

The schedule of observations, examinations, and evaluations is shown in Table 3.1.3-1.

Table 3.1.3-1 Trial Schedule

Procedure (Week) (Day)	Screening period	Treatment period															Post-treatment observation period *1	
		W1 to W8 (once-weekly IMP administration)								W9 to W104 (IMP administration every two weeks)							Completion	Withdrawal
		W1 D1	W2 D8	W3 D15	W4 D22	W5 D29	W6 D36	W7 D43	W8 D50	W9 D57	W11 D71	W13 D85	W15 D99	After Week 17 up to Week 102	W103 D715	W104 D722	11 - 17 days after W 103 D279	Within 7 days from withdrawal judgment
(Allowance)		1	5 - 11	12 - 18	19 - 25	26 - 32	33 - 39	40 - 46	47 - 53	54 - 60	66 - 76	80 - 90	94 - 104	Same as W11 to W15 (up to Week 102)	710 - 720	-	11-17 days after W 103	
Written informed consent	●																	
Subject Information	□																	
Virus test ^{a)}	□																	
Chest x-ray	□																	
hCG pregnancy test ^{b)}	□																	
Body height	□																	
Patient enrollment for this trial		○																
Blood sampling for HLA genotyping		○																
IMP administration ^{c)}		↓ (1)	↓ (2)	↓ (3)	↓ (4)	↓ (5)	↓ (6)	↓ (7)	↓ (8)	↓ (9)	↓ (10)	↓ (11)	↓ (12)	↓ (every 2 weeks) (13-55)	↓ (56)			
Concomitant drug survey		□																
Adverse event observation		□																
Medical interview by (sub) investigator	□	○	○	○	○	○	○	○	○	○	○	○	○	○ (every 2 weeks)	○		□	□
Body weight	□	▲				□				□				□ (every 4 weeks)			□	□
Vital signs ^{d)}	□	▲				○				○				○ (every 4 weeks)			□	□
Hematology test ^{e) f)}	□	▲		○		○		○		○	○	○	○	○ (every 2 weeks)	○		□	□
Peripheral blood smear preparation	□	▲		□		□		□		□	□	□	□	□ (every 2 weeks)	□		□	□
Blood biochemistry test ^{g)}	□	▲				○				○		○		○ (every 4 weeks)			□	□
12-Lead electrocardiogram	□					○				○		○					□	□
QOL (EORTC QLQ-C30)		○				□				□		□		□ (every 4 weeks)			□	□
Performance status (ECOG PS)	□	▲				□				□		□		□ (every 4 weeks)			□	□
Bone marrow aspiration ^{f)}	□																□	□
Bone marrow smear preparation ^{g)}	□																□	□
Urinalysis ^{h)}	□	▲				○				○		○		○ (every 4 weeks)			□	□
Expressed level of WT1mRNA		○				○				○		○		○ (every 4 weeks)			□	□
IFN-γ production (OCV-501 specific, WT1-killer peptide specific)		○				○				○		○		○ (at Weeks 25, 37, 49, 61, 73, 85, 97)			□	□
Anti-501 antibody		○				○				○		○					□	□
Anti-WT1 antibody		○				○				○		○		○ (every 4 weeks)			□	□
Immunoglobulin		○				○				○		○					□	□

●: Obtained before screening examinations.
○: Mandatory (to be performed/collected before IMP administration).
▲: Data from a screening examination can be used if they were obtained within 7 days before the IMP administration (to be performed before IMP administration except peripheral blood smear preparation).
□: Mandatory
^a HIV antibody, HBV-DNA, HCV antibody.
^b To be performed only for female subjects who are capable of becoming pregnant (Urine test).
^c Once-weekly up to the 8th administration, once every two weeks from the 9th administration onward. The subject's general conditions, including injection site reaction, must be observed at the trial site for one hour after IMP administration.
^d Blood pressure, pulse, body temperature
^e Hb, Hct, RBC, WBC, WBC differential (visual count), PLT.
^f If leukemic blast cells appear in peripheral blood or if there is a reduction in blood cell components, perform bone marrow aspiration by post-treatment observation period, and prepare smear.
^g AST, ALT, ALP, LDH, γ-GTP, TP, ALB, T-Bil, BUN,UA, Cr
^h pH and specific gravity, bilirubin, glucose, ketone bodies, white blood cells, occult blood, protein, urobilinogen
*1 Even if treatment is discontinued before completion of the 2-year treatment period, patients will still undergo the post-treatment examination.
(If an AE has not resolved by the end of the post-treatment observation period, the investigator or subinvestigator will explain to the subject the need for follow-up investigation and will request the subject's cooperation. The investigator or subinvestigator will conduct a follow-up investigation within 4 weeks after the post-treatment observation period.)

3.2 Efficacy and Safety Variables

3.2.1 Efficacy

Primary endpoint:

- Disease-free survival (DFS)

Secondary endpoint:

- Overall survival (OS)
- Quality of life (EORTC QLQ- C30)
- Performance status (ECOG PS)

Reference endpoint:

- DFS until OS cutoff date

3.2.2 Safety

AE, hematology tests, blood biochemistry tests, urinalysis, vital signs (blood pressure, pulse rate, body temperature), body weight and ECG

3.2.3 Exploratory variables

OCV-501 specific IFN- γ production, WT1-killer peptide specific IFN- γ production, anti-OCV-501 antibody level, anti-WT1 antibody level, immunoglobulin and WT1 mRNA level

4 STATISTICAL METHODS

4.1 Data Quality Assurance

All tables, figures and data listings to be included in the report will be independently checked for consistency and integrity in accordance with standard PAREXEL procedures.

4.2 General Presentation Considerations

The important terms will be defined as follows:

Term	Definition
Screen failure	A screen failure is a subject from whom written informed consent was obtained, but to whom an IMP was not allocated
Individual subject trial start date	The day of obtaining the subject's written informed consent
Individual subject withdrawal	A subject who discontinue OCV-501 or placebo treatment before completion of the post-treatment observation period
Individual subject trial withdrawal date	The day of the withdrawal examination of the post-treatment observation period within 7 days after the investigator or subinvestigator judged withdrawal to be necessary
Individual subject completion	A subject who complete 2 years of treatment with OCV-501 or placebo, and complete the post-treatment examination at 11-17 days after the end of IMP administration
Individual subject trial completion date	The day of the completion examination at 11-17 days after the end of the 2-year IMP administration period
Individual subject trial period	The period from the day of obtaining the subject's informed consent to the day of trial completion or the day of the withdrawal examination. Does not include the follow-up period nor the outcome survey.

Continuous data will be summarized in terms of the mean, standard deviation (SD), median, minimum, maximum and number of observations, unless otherwise stated. The minimum and maximum will be reported to the same number of decimal places as the raw data recorded in the database. The mean, median, lower quartile and upper quartile will be reported to one more decimal place than the raw data recorded in the database. The SD will be reported to two more decimal places than the raw data recorded in the database. In general, the maximum number of decimal places reported shall be four for any summary statistic.

Categorical data will be summarized in terms of the number of subjects providing data at the relevant time point, frequency counts and percentages. Percentages will be presented to one decimal place. Percentages will not be presented for zero counts. Percentages will be calculated using the number of observations with non-missing values as the denominator.

Changes from baseline in categorical data will be summarized using shift tables where appropriate.

P-values greater than or equal to 0.001, in general, will be presented to three decimal places. However, if a p-value is only presented to four decimal places (by SAS) it will not be rounded again, but will be presented to four decimal places. P-values less than 0.001 will be presented as “<0.001”.

Two sided statistical tests with $\alpha=0.05$ will be performed to test the hypotheses.

95% Confidence intervals (CIs) will be presented to one more decimal place than the raw data. Multiplicity will not be adjusted.

All report outputs will be produced using SAS® version 9.3 or a later version in a secure and validated environment.

Baseline

Baseline is defined as the last available screening or pre-treatment assessment.

Allowance window

Assessments taken outside of protocol allowable windows will be included in the summaries according to the eCRF assessment recorded by the investigator.

Unscheduled assessments

Extra assessments (laboratory data, vital signs or exploratory items associated with non-protocol clinical visits or obtained in the course of investigating or managing AEs) will be included in listings but not summaries.

Discontinuation assessments

Discontinuation assessments will be summarized according to the eCRF assessments recorded by the investigator at the time of discontinuation, not otherwise specified.

Graphs

Graphs will be plotted by “day” or “month” or “Visit timepoint (week)” as specified in the shells.

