4.8.3 Clinical Laboratory Evaluation

1) Definition:

A subject will be defined as having a treatment-emergent laboratory abnormality if any of the following conditions are satisfied for a specific laboratory parameter.

- A laboratory result within the normal range at baseline and either a result below the lower limit of the normal range or above the upper limit of the normal range at any post-baseline time point.
- A laboratory result below the lower limit of the normal range at baseline and a laboratory result above the upper limit of the normal range at any post-baseline time point.
- A laboratory result above the upper limit of the normal range at baseline and a laboratory result below the lower limit of the normal range at any post-baseline time point.

In addition, laboratory values will be graded using CTCAE version 4.03.

2) Analysis Set:

SS

3) Analysis Method:

The following summaries will be generated:

- A summary of each laboratory parameter and its change from baseline by treatment arm and time point

- Shift table of laboratory parameter (Urinalysis) at each post-baseline point
- A summary of the number and percentage of subjects experiencing low, normal and high values at baseline and at each post-baseline time point (shift table)
- A summary of the number and percentage of subjects with different CTCAE grades at baseline, at each post-baseline time point and worst grade in post-baseline (shift table)
- A summary of new or worsened laboratory abnormalities based on CTCAE Grades (Categories: all grades, Grade 1+Grade 2, Grade 3+Grade 4)
In this table, the worst grade observed in post-baseline are summarised. Patients with no change or better grade from baseline are not counted. 'New' abnormality means 'grade 0' at baseline and '>= grade 1' after baseline. All grade means '>= grade 1' after baseline.

By-subject listings of all laboratory data will be generated by treatment arm with reference range provided and abnormal values will be marked with flags (H/L, Gx).

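### SAP 4.2 keeps unscheduled and AE-driven laboratory values out of all summaries, so the two worst-grade laboratory tables in SAP 4.8.3 can understate graded toxicity

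*SAP*

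**What the plan says.** SAP 4.2, under unscheduled assessments, defines the values concerned: "Extra assessments (laboratory data, vital signs or exploratory items associated with non-protocol clinical visits", or those "obtained in the course of investigating or managing AEs) will be included in listings but not summaries". No exception is attached.

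Two neighbouring rules in SAP 4.2 keep other values in. On timing: "Assessments taken outside of protocol allowable windows will be included in the summaries according to the eCRF assessment recorded by the investigator". On stopping: "Discontinuation assessments will be summarized according to the eCRF assessments recorded by the investigator at the time of discontinuation".

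SAP 4.8.3 lists the laboratory outputs. One is a CTCAE shift table covering grades "at each post-baseline time point and worst grade in post-baseline (shift table". Another covers new or worsened abnormalities by grade band, of which the SAP says: "In this table, the worst grade observed in post-baseline are summarised". The section also defines a treatment-emergent laboratory abnormality, for a subject normal at baseline, as a result "below the lower limit of the normal range or above the upper limit of the normal range at any post-baseline time point". On listings it says: "By-subject listings of all laboratory data will be generated by treatment arm with reference range provided", with abnormal values flagged by direction and grade.

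**The concern.** Leaving unscheduled results out of by-visit means and by-visit shift tables is ordinary practice, since those tables describe a fixed set of time points. A worst-case table has a different purpose: it should report the most severe value each patient had at any time on study. Samples drawn because a patient is unwell are plausible candidates for that value. This is an inference; the documents do not state it.

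Under the SAP 4.2 rule, take a patient whose creatinine reaches a high grade at an unscheduled visit and recovers before the next planned draw. That patient is counted at the lower grade, in a table whose label says it shows the worst grade observed. Characterizing and comparing safety is a stated secondary objective (Protocol 2, SAP 2), and these two tables are the plan's worst-grade laboratory toxicity summaries by CTCAE grade.

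**Working it through.** The plan gives no figure on this point to reproduce. The check has a textual part and an illustrative part.

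**Does the rule reach the two tables?**

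1. SAP 4.2 excludes the values from summaries in general, not from by-visit summaries only.
2. SAP 4.8.3 introduces its outputs as summaries, and the descriptions of the worst-grade shift table and the new-or-worsened table each begin by calling the table a summary. The exclusion therefore applies to them on its face.
3. SAP 4.8.3 has no sentence overriding SAP 4.2. The discontinuation rule in SAP 4.2 carries a qualifier that leaves room for other specifications; the unscheduled rule carries none.
4. The SAP 4.13 table of changes from the protocol does not mention the exclusion, and Protocol 11.3.2 contains no such exclusion.

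**Direction.** With baseline fixed, let S be a patient's set of scheduled, completion and discontinuation grades after baseline, and U the set of unscheduled grades. The tables use max(S), while the label promises max(S and U together). Since max(S) ≤ max(S and U together) for every patient, the error runs one way only, towards lower grades.

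**Size (illustration).** Inputs:

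- Scheduled hematology interval g = 14 days (Protocol 7.2.1.1 and Table 7.1-1).
- Scheduled biochemistry interval g = 28 days (Protocol 7.1.3.2.2 and Table 7.1-1; Day 1, Day 29, Day 57, Day 85, then every 4 weeks).
- Time at the worst grade, d days: not given in the documents, so assumed and varied.
- Onset assumed uniform between draws, and visits assumed on their target days.

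Probability that the excursion misses every scheduled draw = 1 − min(1, d/g).

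| d (days, assumed) | Biochemistry, g = 28 | Hematology, g = 14 |
|---|---|---|
| 3 | 1 − 3/28 = 89% | 1 − 3/14 = 79% |
| 7 | 1 − 7/28 = 75% | 1 − 7/14 = 50% |
| 10 | 1 − 10/28 = 64% | 1 − 10/14 = 29% |
| 14 | 1 − 14/28 = 50% | 0% |
| 21 | 1 − 21/28 = 25% | 0% |

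These are not estimates of the bias. If q is the chance that an unscheduled sample was drawn during the excursion, the rule removes information with probability q × (1 − min(1, d/g)). At d = 7 this runs from 0 (q = 0) to 75% for biochemistry or 50% for hematology (q = 1). An excursion with no unscheduled sample is lost under either rule. A table cell changes only if the unscheduled grade also exceeds every retained post-baseline grade for that patient and, in the new-or-worsened table, moves the patient into a counted category. The documents give neither q nor d.

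**The case against.** The strongest reply is that little is really lost. Every laboratory value is listed with flags. An abnormal laboratory finding can be an AE (Protocol 8.1.1), clinically significant events found at interview are evaluated as AEs (Protocol 7.2.2.5), and SAP 4.8.2 tabulates TEAEs by arm and CTCAE grade, including maximum grade. Patients who stop treatment have a withdrawal examination within 7 days, with hematology and biochemistry where feasible (Protocol 7.1.4.2), and those results are summarized.

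All of this stands as mitigation, and it makes the loss partial. It does not close the gap. Listings give no rates by arm. AE reporting depends on investigator judgment, and Protocol 8.3.1 records the diagnosis rather than its individual symptoms where a diagnosis can be made. The withdrawal examination does not help for AEs investigated between visits in patients who continue treatment.

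It can also be argued that a specific section governs a general one, or that the table shells settle the matter. The SAP states no such precedence, and SAP 4.2 mentions shells only for graphs.

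A reader might infer more than the text supports:

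- **A distorted comparison between arms.** The same rule applies to both blinded arms, and nothing in the documents shows a differential effect.
- **The worst post-baseline ECG shift table in SAP 4.8.4 is also affected.** The SAP 4.2 rule names laboratory data, vital signs and exploratory items, not ECG.
- **A planned table of treatment-emergent laboratory abnormality is damaged.** SAP 4.8.3 defines the term, but none of its listed summaries uses it by name.
- **Short renal or blood-count excursions are expected because WT1 is expressed in kidney and hematopoietic progenitors (Protocol 1.1).** That passage reports expression, not toxicity. Protocol 1.2.2 reports no dose-limiting toxicity in phase 1.

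**Conclusion.** The concern holds for two laboratory tables: the worst post-baseline CTCAE grade shift table and the new-or-worsened abnormality table. Read with SAP 4.2, both report the worst grade among scheduled (including out-of-window), completion and discontinuation values, which is narrower than their descriptions promise. The error can only lower reported toxicity.

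Its size cannot be derived from the documents. The 75% and 50% figures for a 7-day excursion are upper limits, resting on an assumed duration, uniform onset and on-target visits. Hematology excursions of 14 days or more are always caught by a scheduled draw under the same assumptions. The primary endpoint is not affected. The point is worth correcting because the remedy is small and the data are already collected and listed.

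**What to change.** In SAP 4.2, restrict the exclusion. Suggested wording: *Unscheduled results are listed and are not included in by-visit summaries.*

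In SAP 4.8.3, add: *All post-baseline laboratory values, scheduled and unscheduled, are used to derive the worst post-baseline CTCAE grade and new or worsened abnormalities, and treatment-emergent laboratory abnormality wherever it is tabulated.*

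The cost is this short SAP edit and one programming flag, with no new data collection. Reported laboratory toxicity rates may come out slightly higher than under the current rule.
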